1. BACKGROUND

X-ray mammography has significantly reduced breast cancer mortality. However, even with mammography, many breast cancers are not detected until they are advanced, and illness and death due to breast cancer is a major problem. The best way to control breast cancer is to detect it at an early stage when it is relatively easy to treat. MRI has potential to significantly improve sensitivity to cancer, and detect many cancers years earlier than mammography, especially in women with dense breasts. Given the great sensitivity of MRI, it is likely that properly designed MRI screening would detect almost all invasive cancers and many pre-invasive cancers at an early stage, resulting in tremendously decreased mortality and illness. Effective MRI-screening would have an exceptional impact in the region surrounding the University of Chicago Medical Center, where rates of breast cancer are unusually high, with an especially high prevalence of aggressive breast cancer. If MRI screening can identify cancers several years earlier than conventional methods – with very few ‘false positives’ - this would have tremendous benefits for patients.

Mammography is not very effective in women with dense breasts and these women currently do not have good options for screening. Even in women with normal breast density – mammography often does not detect cancers until they are fairly large. It would be much better to detect cancer early when it is easier to cure. This is especially important for women who are at high risk for aggressive breast cancer. MRI has very high sensitivity, and has potential to detect cancer earlier than conventional mammography [1]. Sensitivity of MRI is not affected by breast density [1]. However,

there are concerns that MRI lacks the specificity required for screening large numbers of women, and will generate an unacceptable number of false positives, producing unnecessary stress, inconvenience, and expense. In addition, there are concerns that even if the accuracy of MRI can be significantly improved, MRI is too expensive for screening in the general population.

Routine screening for breast cancer with X-ray mammography has significantly reduced morbidity and mortality [1], and clearly demonstrated the benefits of early detection. While X-ray mammography is effective for many women – there is concern that it does not provide adequate screening for large groups of women. In women with dense breasts, the sensitivity of mammography to early cancers is reduced by 30-50% [5, 6]. This is particularly problematic because women with dense breasts are at higher risk for aggressive breast cancers [7]. In fact, there is concern that for all women at increased risk for aggressive breast cancer, e.g. triple negative breast cancer, X-ray mammography does not always detect cancer early enough [1]. Much earlier detection is likely to substantially decrease morbidity and mortality.

2. PURPOSE/HYPOTHESIS

We propose to test an innovative MRI breast cancer screening protocol in women with mammographically dense breasts as well as other women with moderately increased cancer risk. MRI, combined with other methods of risk assessment, has potential to significantly improve sensitivity to cancer in dense breasts and detect cancer in all cases at a much earlier stage, with far fewer interval cancers than mammography [8, 9].

Previous tests of MRI sensitivity show that this screening could significantly increase the likelihood of detecting invasive cancers resulting in decreased mortality from breast cancer [1]. Effective MRI-screening would have an exceptional impact in the region surrounding the UC Medical Center, where rates of breast cancer are unusually high, and where the prevalence of aggressive breast cancer is also very high. If MRI screening can identify breast cancers, particularly the most aggressive subtype of breast cancer, several years earlier than conventional methods, this would have tremendous benefits for patients.

We propose to develop fast, accurate, quantitative, and inexpensive MRI screening methods that can easily be implemented in routine clinical practice. This research will build on innovative work from this team that has significantly advanced breast MRI, including dynamic contrast enhanced MRI of the breasts. This is an opportunity for the University to have a significant impact, initially in our immediate neighborhood, and eventually nationally and internationally. This is an area where the University should lead because of the devastating effect of breast cancer in south Chicago.

The specific purpose of the study is as follows:

1. Develop an efficient, quantitative MRI-screening protocol, less than 15 minutes in duration. Evaluate signal-to-noise ratio and reproducibility in 10 volunteers with dense breasts.

2. Scan approximately 50 women with mammographic or sonographic findings that require biopsy using the short MRI protocol (15 minutes), to establish reasonable cutoffs for MRI parameters derived from the short protocol, that are likely to identify benign and malignant lesions with high sensitivity.
3. In partnership with the Cancer Risk Clinic and the Breast Center, we will identify and recruit 150 women with dense breasts and/or intermediate risk of breast cancer who will also undergo the short MRI protocol.
4. Perform a reader study to evaluate false positive rate, based on the cutoffs established in women with biopsy proven benign and malignant lesions.
5. Perform quantitative analysis to determine standard DCEMRI protocols including Ktrans (the rate constant for contrast media uptake; [2-4]). In addition, we will test novel parameters that can be extracted from ultrafast datasets; initial time of enhancement in parenchyma and suspicious lesions, new approaches to calculating Ktrans and the arterial input function based on early enhancement, and number and size of arteries feeding suspicious lesions and rate of enhancement of those blood vessels. These markers can be accurately calculated from ultrafast imaging but cannot be accurately measured with conventional methods. Determine the rate of false positives based on the cutoffs for each of these parameters determined from the study of women with confirmed breast cancer ('2' above).
6. Suspicious lesions will be defined by the clinical interpretation of the breast MRI images performed by the attending breast radiologist. Based on the radiologist determination that the MRI findings are suspicious (these findings include masses, non-mass enhancement and foci), suspicious lesions will be assigned a Bi-Rads code specifying whether additional work up or biopsy is necessary. These are BiRads codes 0, 4 and 5. False positive diagnosis should be minimized as all attending physicians reading breast MRI at this institution are fellowship trained in breast imaging.

3. RECRUITMENT PLAN

We plan to enroll approximately 200 subjects in total.

1. We will scan approximately 200 women who meet the entry requirements described below. This number may vary slightly because we will scan women with suspicious findings on mammography until we find 30 cancers, verified by the subsequent biopsy. Therefore it is not possible to report the exact number of women who will be in this group.
2. We will scan 150 healthy women with dense breasts and/or women who have risk of breast cancer that is average or higher.

Dense breasts are defined as categories C and D, defined in the American College of Radiology (ACR) BiRads manual. We will also follow ACR guidelines for risk categories. The ACR defines intermediate risk as those patients with a lifetime risk for breast cancer of 15%-20%. This includes women with a personal history of breast cancer, history of proven lobular neoplasia, atypical ductal hyperplasia or other women with 15%-20% risk based on risk models.

4. ELIGIBILITY.

Inclusion criteria:

- Women who have a mammographically and/or sonographically identified finding that will require image guided biopsy.
- OR
- For the ‘screening group’ we will recruit women between ages of 30 –70 who have above 10% lifetime risk of breast cancer or who have dense breasts (based on BIRADS score) but who currently do not have any diagnosis of breast cancer.
- We will select women for the screening group and the group of women with suspicious mammographic findings so that the two groups are well-matched. Our target is to match the percentage of parous and non-parous women, and premenopausal and post-menopausal women. In addition we will match the age distribution in the two groups.

Exclusion criteria:

- Women with a history of adverse reactions to contrast media.
- Women who are pregnant.
- Patients who are demonstrated to be at risk for an allergic reaction or nephrogenic systemic fibrosis (NSF) will be excluded from the study. Details as to how patients are evaluated for these risks are provided below (see ‘Potential Risks’).

5. STUDY DESIGN.

Enrollment:

1. Approximately 50 women with suspicious findings on mammography who are scheduled for biopsy will be recruited. We expect this will result in 30 cancers and 20 benign lesions. **When possible**, we will perform MRI scans before the biopsy so that biopsy will not affect MRI results. Lesions will be classified as benign and malignant based on the subsequent biopsy. We will continue scanning until we have scanned 30 women with biopsy-confirmed malignancy. We estimate that

this will require a total of 50 scans, but the total number may turn out to be slightly higher or slightly lower.

2. We will also recruit 150 women with dense breasts and/or women who have intermediate risk of breast cancer for this study.

MRI scans:

Women will receive a mammogram and an MRI-screening exam. The MRI screening exam will consist of calibration scans, bilateral T2-weighted scans, and a DCEMRI scan. The duration of the entire protocol will be less than 15 minutes.

Ground truth assignment:

Assignment for the group who will have biopsy based on mammogram and/or ultrasound:

- a. **Surgical pathology will be the gold standard for these patients for the lesions previously identified on mammogram or ultrasound.**
- b. **Any additional lesions detected on MRI will follow the assignment as below for the screening group.**

Assignment for the dense breast/intermediate risk group:

- a. Women who have no cancer found on MRI will be classified as having no cancer.
- b. If additional lesions are deemed suspicious on MRI and these lesions are biopsied, they will be classified as benign or malignant based on biopsy surgical pathology results.
- c. If additional lesions are found on MRI but physicians elect not to biopsy based on the findings, these lesions will be assumed to be benign for the purposes of this study. In some cases, women may be referred for follow-up exams, e.g. in 6 months. In these cases, lesions that are still not biopsied after 6 month follow-up will be assumed to be benign for the purposes of this study.

Reader Study:

The T2-weighted scans and high resolution post contrast T1-weighted scans will be evaluated by Radiologists using conventional diagnostic procedures. Radiologists will also evaluate ultrafast scans to identify regions with anomalously rapid enhancement, or abnormally enhancing blood vessels in ultrafast images. Based on this evaluation they will assign a probability of malignancy, on a scale from 1 – 10. Three independent readers will evaluate images and assign a probability of malignancy. We will calculate ROC curves for each of the 3 readers to assess 1) variability of Reader's 'probability of malignancy' scores 2) AUCs for Radiologists compared to the quantitative parameters described above. The Reader study is an exploratory aim and the study is not powered to perform this analysis with reasonable statistical confidence. The goal is simply to obtain

a preliminary assessment that can provide a basis for future studies with a larger number of patients and readers.

Statistical Power:

Thirty women with biopsy-confirmed breast cancer and between sixty and seventy controls (women with dense breasts and/or moderate breast cancer risk, frequency-matched by parity, age, and menopausal status; control group also includes some women with biopsy-proven benign lesions) will be scanned using the short MRI protocol. Receiver Operating Characteristic (ROC) curves and statistics will be constructed for several MRI parameters of interest: Ktrans, initial time of enhancement in parenchyma and suspicious lesions, new approaches to calculating Ktrans and the arterial input function based on early enhancement, and number and size of arteries feeding suspicious lesions and rate of enhancement of those blood vessels. The primary endpoints of this study are Ktrans and 'initial time of enhancement'. Optimal diagnostic thresholds will be determined for each parameter, where the optimal threshold for a given parameter is defined as the parameter value which has highest sum of specificity and sensitivity over all possible thresholds with specificity > 80%. We will also test whether the area under the curve (AUC) for each parameter exceeds 60%. 95% confidence intervals will be constructed for the AUC for each curve and the sensitivity and specificity of each optimal threshold. For our two primary endpoints (Ktrans and initial time of enhancement), our sample of 200 subjects (30 cases + 170 controls) is large enough to detect AUCs of 74% (i.e., a difference of 14%) at the 5% significance level.

Thresholds determined in this pilot study will later be validated in a larger cohort – this is the subject of an RO1 proposal to be submitted soon. In the future cohort, we will construct covariate-adjusted ROC curves that will be used to calculate thresholds, specificities, and sensitivities for patients with different breast cancer risk factors (Gail scores, family history, etc.).

We will also produce ROC curves for each reader in the 'reader study' to obtain a preliminary estimate of how standard evaluation of abbreviated MRI datasets compare with the quantitative analysis described above. However, this is an exploratory aim of the study and the study is not powered to evaluate the statistical confidence of these measurements.

6. PROCEDURES TO WHICH HUMANS WILL BE SUBJECTED:

Patients with lesions detected on mammography or ultrasound:

Patients with scheduled biopsy will undergo the research MRI prior to their biopsy. At the time that the biopsy is recommended, the radiologist will identify the patient as one who will be having a biopsy and could qualify for research MRI. The breast care treatment teams (high risk clinic, surgery clinic) will contact the Radiology Research Coordinator if they have a patient that they believe could be eligible for the study. Once identified, the patient's name and MRN will be given to the research coordinator. She will be contacted by phone regarding the research study by the research coordinator. The

study will be explained to her, and she will be asked about her interest in participating. Questions, if any, will be answered. If interested, she will be scheduled in an MRI time slot. Biopsy patients will be scheduled for their MRI in the same visit unless they prefer otherwise. Prior to the MRI, they will be asked to read and sign the informed consent document by the research coordinator.

Data will be collected from the subjects regarding their race and ethnicity, age, weight, height, menopausal status, last menstrual cycle date.

All routine precautions will be taken prior to the MRI scans (screening for metallic or electronic (e.g., pace-maker) implants, removal of all metallic objects, etc.).

Patients with dense breasts and those referred for intermediate risk:

Women age 30-60 with dense breasts presenting for screening mammography are one of the target populations. The radiologist will identify scheduled mammography screening patients who are known to have mammographically dense breasts based on prior screening mammograms. Once identified, the patient's name and MRN will be given to the research coordinator. In cases identified by the Breast Center or Cancer Risk Clinic as intermediate risk, the research coordinator will be contacted about the patient.

The patient group who has dense breasts will be recruited by the Radiology Research Coordinator. Recruitment will be based upon the fact that the patient, who is scheduled for a screening mammogram, is known to have dense breasts on a previous years screening mammogram. Based on her known breast density, she will be eligible for recruitment into the study. Once a patient with dense breasts or intermediate risk is identified, she will be contacted by phone or in person during a clinic visit regarding the research study by the research coordinator. The study will be explained to her, and she will be asked about her interest in participating. Questions, if any, will be answered. If interested, she will be scheduled in an MRI time slot. Mammography patients will be scheduled for their MRI in the same visit unless they prefer otherwise. Prior to the MRI, they will be asked to read and sign the informed consent document by the research coordinator.

Data will be collected from the subjects regarding their race and ethnicity, age, weight, height, menopausal status, last menstrual cycle date.

- 1) Patients undergoing a screening or routine diagnostic mammogram will also undergo an MRI exam on the same day. The mammography exams will be part of standard clinical care, and not acquired specifically for the purpose of this study. The MRI exams will be research-only exams.
- 2) Blood test of kidney function (standard screening procedure) for breast MRI w/contrast is only required if: over 60 years old, have hypertension or diabetes.

All routine precautions will be taken prior to the MRI scans (screening for metallic or electronic (e.g., pace-maker) implants, removal of all metallic objects, etc.).

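### Recruitment Plan item 1 puts about 200 women where the rest of the plan puts about 50, and the power section gives two control counts (60–70 and 170)

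*Combined protocol and SAP*

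**What the plan says.** Section 3 (Recruitment Plan) opens with the total: "We plan to enroll approximately 200 subjects in total". Two numbered items follow.

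- Item 1: "We will scan approximately 200 women who meet the entry requirements described below". Its next sentences are "This number may vary slightly because we will scan women with suspicious findings on mammography until we find 30 cancers, verified by the subsequent biopsy" and "Therefore it is not possible to report the exact number of women who will be in this group".
- Item 2: "We will scan 150 healthy women with dense breasts and/or women who have risk of breast cancer that is average or higher".

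Section 5 (Study Design, Enrollment) has the same two-item layout with a different first number: "Approximately 50 women with suspicious findings on mammography who are scheduled for biopsy will be recruited". It expects 30 cancers and 20 benign lesions from them, allows the count of 50 to move slightly either way, and adds 150 screening women. Section 2 (Purpose/Hypothesis, items 2 and 3) also gives about 50 and 150.

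Section 5 (Statistical Power) opens with "Thirty women with biopsy-confirmed breast cancer and between sixty and seventy controls". It describes the controls as frequency-matched and as including some women with biopsy-proven benign lesions. The same paragraph then bases the detectable AUC of 74%, against 60%, on 200 subjects made up of 30 cases and 170 controls. It gives a 5% significance level but neither the power nor whether the test is one-sided.

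**The concern.** The Recruitment Plan is where study staff and an ethics board look for the number of women to be scanned. Its two numbered items do not add to the total printed directly above them, and the first item differs fourfold from the size given for the same group in Sections 2 and 5.

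The control count matters for a different reason. It is an input to the only sample-size justification in the plan, and it has two values in one paragraph. A reader cannot tell whether the primary ROC analysis of Ktrans and initial time of enhancement uses all 170 non-cancer women or a matched set of 60–70. That choice changes both the precision of the AUC and who the controls are.

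**Working it through.** **1. Group sizes**

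| Source | Biopsy group | Screening group | Sum |
|---|---|---|---|
| Section 2, items 2 and 3 | about 50 | 150 | 200 |
| Section 5, Enrollment | about 50 (30 malignant + 20 benign) | 150 | 200 |
| Section 5, Statistical Power, detectable-AUC sentence | 30 cases + 170 controls | – | 200 |
| Section 3, items 1 and 2 as printed | about 200 | 150 | 350 |

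The stated total of 200 is reproduced three ways: 50 + 150, 30 + 20 + 150, and 30 + 170, where 170 = 20 + 150. Only Section 3 fails: 350/200 = 1.75.

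**2. Can item 1's 200 be a biopsy-group size?** Thirty cancers in 50 women is a yield of 30/50 = 60%, which agrees with the expected 30 malignant and 20 benign. Thirty in 200 would be 15%, which agrees with nothing else in the plan. The allowance for slight variation does not cover 50 against 200.

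**3. The two control counts.** I used the Hanley-McNeil variance for an AUC of A with m cases and n controls:

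Var(A) = [A(1−A) + (m−1)(a−A²) + (n−1)(b−A²)] / (mn), where a = A/(2−A) and b = 2A²/(1+A).

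- At A = 0.60: A(1−A) = 0.2400, a−A² = 0.0686, b−A² = 0.0900.
- At A = 0.74: A(1−A) = 0.1924, a−A² = 0.0397, b−A² = 0.0818.

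For m = 30 and n = 170:

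- SE at 0.60 = √[(0.2400 + 29×0.0686 + 169×0.0900)/5100] = 0.0585.
- SE at 0.74 = √[(0.1924 + 29×0.0397 + 169×0.0818)/5100] = 0.0545.
- One-sided 5%, null SE in the critical value: Φ[(0.14 − 1.645×0.0585)/0.0545] = Φ(0.80) = 79%.
- One-sided 5%, alternative SE throughout: Φ[0.14/0.0545 − 1.645] = Φ(0.92) = 82%.

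The plan's 74% is therefore reproduced at 30 + 170 if a one-sided 5% test with about 80% power was intended. The same formulas for the other counts, with the range running over the two SE conventions, give:

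| Cases + controls | One-sided 5% | Two-sided 5% |
|---|---|---|
| 30 + 60 | 72–77% | 59–67% |
| 30 + 70 | 73–78% | 61–68% |
| 30 + 170 | 79–82% | 68–73% |
| 30 + 320 | 81–84% | 71–75% |

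The AUC detectable with 80% power, one-sided, solves A − 0.60 = 1.645×SE + 0.842×SE(A). With the null SE in the first term it is 0.742 for 170 controls, 0.752 for 70 and 0.755 for 60. With SE(A) in both terms it is 0.736, 0.743 and 0.745.

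The last row of the table (350 women, 30 of them cases) tests whether item 1's number matters to power. With cases held at 30, 150 further controls add about 1 to 2 points one-sided.

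**The case against.** **Item 1 may be restating the total.** Its first sentence does not name the biopsy group. It refers to the entry requirements, and Section 4 covers both groups. On that reading 200 repeats the line above, varies slightly because the biopsy part runs to 30 cancers, and already contains item 2's 150, leaving 50. This is a fair reading, and it means 350 cannot be presented as the plan's intention. It does not clear the text. Item 1 is the first of two parallel numbered items, its explanation concerns only women with suspicious findings, and it calls them one group. If 200 is the total, item 2 sits inside item 1 and Section 3 never gives the biopsy-group size.

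**The rest of the plan is clear.** This is true: Sections 2 and 5 and the detectable-AUC sentence agree on 200, so the error can be recovered from the document.

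**Two stronger inferences do not stand.** A reader might infer that 200 biopsy women at a 60% yield would bring in about 120 cancers (200 × 0.60). That cannot happen under the plan, because scanning in this group stops at 30 cancers. A reader might also infer that item 1 upsets the detectable AUC. It does not: that statement rests explicitly on 30 + 170.

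**The control-count conflict may be harmless.** The 60–70 could be a matched subset of the 170, but the plan does not say so. The loss in power is modest because 30 cases limit the precision. With the alternative SE throughout, the detectable AUC for 60–70 controls still rounds to 74% (0.743–0.745). The arithmetic therefore does not exclude 60–70 under every convention. What stands is that the sentence names 170, and only 170 brings power at 0.74 to about 80%.

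**Conclusion.** Wrong as written, in two places, and worth correcting. Neither defect is fatal to the design.

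1. Section 3, item 1 either overstates the biopsy group fourfold (200 against about 50, making 350 against a total of 200) or restates the total in a place where a group size belongs. Both readings need a correction. The documents do not show an intention to enrol 350, and item 1 has no effect on the case count or the detectable AUC.
2. The Statistical Power text contradicts itself on the controls. If only 60–70 are analysed, power at an AUC of 0.74 is about 72–78% rather than 79–82%, and the sample is 90–100 women rather than 200. These figures assume a one-sided 5% test and the Hanley-McNeil variance. Two-sided, they are about 59–68% and 68–73%.

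**What to change.** - **Section 3, item 1:** replace the figure with about 50 women with suspicious findings, scanned until 30 cancers are confirmed by biopsy. Sections 2, 3 and 5 then all give 50 + 150 = 200.
- **Section 5, Statistical Power, opening sentence:** give the controls as about 170 (20 benign + 150 screening), matching the detectable-AUC sentence. If only 60–70 matched controls are to be analysed, say so, say how they are chosen from the 170, and restate the detectable AUC for that number.
- **Same paragraph:** state the power and whether the test is one- or two-sided, so that the 74% can be checked.
- **Section 2, item 1:** while amending, say whether the 10 volunteers with dense breasts are among the 150, since the total depends on it.

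The cost is a short text amendment. No new design decision or recalculation is needed if 170 is the intended count. Choosing 60–70 requires one recalculation.

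### Breast density is a route into the screening group only and is neither matched on nor adjusted for, so the AUC > 60% test may be confounded by density

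*Combined protocol and SAP*

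**What the plan says.** **Entry (Section 4).** The biopsy group, which supplies the cancers, is defined as "Women who have a mammographically and/or sonographically identified finding that will require image guided biopsy", with no density criterion. The screening group consists of women aged 30 to 70 "who have above 10% lifetime risk of breast cancer or who have dense breasts (based on BIRADS score"). Section 6 adds that the dense-breast women are approached because an earlier mammogram showed dense breasts.

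**Matching (Sections 4 and 5).** "We will select women for the screening group and the group of women with suspicious mammographic findings so that the two groups are well-matched". The factors are then named: "Our target is to match the percentage of parous and non-parous women, and premenopausal and post-menopausal women", plus the age distribution. Under Statistical Power in Section 5 the controls are "frequency-matched by parity, age, and menopausal status; control group also includes some women with biopsy-proven benign lesions". Neither list contains density.

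**Data (Section 6).** The same list of subject data is given for both groups: race and ethnicity, age, weight, height, menopausal status and last menstrual cycle date. It names neither density nor parity, although parity is a matching factor.

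**Analysis (Section 5, Statistical Power).** "We will also test whether the area under the curve (AUC) for each parameter exceeds 60" percent. The primary parameters are Ktrans and initial time of enhancement, and the latter is also measured in parenchyma. Covariate-adjusted ROC curves are planned only for a future cohort; Gail scores and family history are given as examples of covariates, and density is not named.

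**The concern.** The one characteristic that is an entry route for one group and not for the other is missing from the matching and from this study's analysis. Of the 200 women, about 50 come through biopsy ("We expect this will result in 30 cancers and 20 benign lesions") and 150 through the screening group, so 150 of the 170 controls have an entry route related to density and none of the 30 cancers does.

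If Ktrans or enhancement time differs between dense and non-dense breasts, part of the unadjusted AUC reflects how women were recruited. Upward bias makes the 60% hurdle too easy to clear. Downward bias hides a useful parameter. The result decides which parameters and thresholds go forward to the larger cohort.

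**Working it through.** **1. The plan's own figure.** Section 5 states that 30 cases and 170 controls can detect an AUC of 74% against 60% at the 5% level. The Hanley-McNeil variance is [A(1-A) + 29(Q1-A²) + 169(Q2-A²)]/(30×170), with Q1 = A/(2-A) and Q2 = 2A²/(1+A).
- A = 0.60: (0.240 + 1.989 + 15.210)/5100, SE 0.0585.
- A = 0.74: (0.192 + 1.151 + 13.829)/5100, SE 0.0545.
- One-sided 5% power: Φ((0.14 - 1.645×0.0585)/0.0545) = 78.9% (binormal variance: 81.1%).

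So 74% reproduces for a one-sided test with about 80% power. The figure is not at fault here; it presumes an unconfounded AUC.

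**2. A marker with no diagnostic value.** The documents give no density shares and no relation between density and the markers. Assumed: 50% of biopsy women dense, a fraction p of screening women dense, and a marker shift of d = 0.5 or 1 SD in dense breasts, towards benign values. The dense share among controls is c = (150p + 10)/170, and

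AUC = 0.5 + (c - 0.5)(Φ(d/√2) - 0.5), where the last bracket is 0.138 for 0.5 SD and 0.260 for 1 SD.

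| p | c | AUC, 0.5 SD | AUC, 1 SD |
|---|---|---|---|
| 50% | 0.500 | 0.500 | 0.500 |
| 60% | 0.588 | 0.512 | 0.523 |
| 80% | 0.765 | 0.537 | 0.569 |
| 100% | 0.941 | 0.561 | 0.615 |

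If the shift runs the other way, the values are 1 minus these. An AUC of 0.60 needs c - 0.5 = 0.10/0.260 = 0.384, which is p of about 94% with a 1 SD shift. Section 5 also mentions 60 to 70 controls in total; with those, the range over p = 60-100% is 0.51-0.59.

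**3. The test when the within-density AUC is 0.60.** 4,000 simulated trials per scenario, DeLong standard error, two-sided 5% assumed. With no density effect, AUC > 60% is concluded in 3-4% of trials. With upward bias (0.5 SD, 1 SD) the chance is 5% and 4% at p = 60%, 11% and 18% at 80%, and 20% and 48% at 100%.

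**4. Power when the within-density AUC is 0.74.** The same simulated test has 77-80% power with no density effect. (Its standard error is estimated at the observed AUC, where it is smaller than at 0.60.) Pooling over density costs power even when both groups have the same density mix. At 50% dense in both, with case mean μ = √2·Φ⁻¹(0.74) = 0.910,

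AUC = 0.5×0.74 + 0.25[Φ((0.910+d)/√2) + Φ((0.910-d)/√2)] = 0.734 (0.5 SD) or 0.717 (1 SD).

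Power is then about 74% or 64%, and those are the right comparators for the effect of imbalance.

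| Screening women dense | Power, 0.5 SD | Power, 1 SD |
|---|---|---|
| 50% (equal mix) | 74% | 64% |
| 60% | 68% | 47% |
| 80% | 53% | 20% |
| 100% | 36% | 5% |

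At 60% dense and 1 SD, the fall from about 80% to 64% is due to pooling (16 points) and from 64% to 47% to imbalance (17 points).

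**5. Cutoffs.** Section 2 (aims 2, 4 and 5) derives cutoffs from the biopsy group of about 50 women and then applies them to estimate false positives. Malignant and benign lesions there share one entry route, so entry by density does not separate them. Section 5 chooses thresholds on ROC curves of cancers against mixed controls, where it can. The two descriptions differ.

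**6. Whether adjustment works.** When nearly all screening women are dense, the non-dense controls are nearly all women with a benign lesion. With no density effect and a benign-lesion shift of 0.5 SD (assumed), a plain density adjustment fitted to all controls moves the AUC from about 0.73 to about 0.68 at p = 100%. The adjustment must therefore keep benign-lesion effects apart from density effects.

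**The case against.** The other side has real weight. The study is a pilot, its thresholds are to be validated later, and leaving covariate adjustment to the next cohort is a declared choice. Screening women may also enter on risk alone, so 100% dense is a boundary case; the most extreme figures above all need it together with a 1 SD shift. At 60% dense, the AUC of a useless marker moves by only 0.01-0.02. These points limit the severity; they do not remove the problem. Section 1 says MRI sensitivity does not depend on density, but that concerns detection, not the values of Ktrans or enhancement time.

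Four stronger readings are tempting and are not supported:
- *The study cannot tell whether its result is affected.* The Section 6 list covers data gathered from subjects and need not be complete: parity is missing too, yet matching requires it. Section 5 says "Women will receive a mammogram and an MRI-screening exam", and Section 6 places mammography in standard care, so density can be retrieved. The gap is that nothing commits the study to recording or using it.
- *The cutoffs are confounded as well.* This holds only under the Section 5 derivation, not under Section 2.
- *All the lost power is due to recruitment.* Step 4 shows that part of it is attenuation from pooling.
- *The two matching statements contradict each other.* Section 4 matches screening women to the whole biopsy group, and Section 5 does not spell out the reference. That is a matter of wording only.

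**Conclusion.** The concern holds as a possibility that the design creates and the analysis leaves unchecked. The AUC > 60% test may be confounded by density, in either direction and by an unknown amount. A reader might infer that the AUC will be inflated; the documents do not support that, because they give neither the density imbalance nor its relation to the markers. If either is absent, there is no confounding.

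Under the stated assumptions the distortion is negligible to small when 60% of screening women are dense. At 80% it is large enough to matter: false conclusions rise from 3-4% to 11-18%, or power falls from 74% to 53% (0.5 SD) and from 64% to 20% (1 SD). The remedy is a cheap improvement to the plan. It is not a reason to doubt the design as a whole.

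**What to change.** 1. Record BI-RADS density from the existing standard-care mammogram, and parity, for every woman. Tabulate both for cancers, benign biopsies and screening women.
2. Keep the unadjusted AUC primary. For Ktrans and initial time of enhancement, prespecify a secondary AUC adjusted for density, age, menopausal status and parity. Model the parameter in the controls, either with an indicator for benign-biopsy versus screening controls or in screening women only. Remove from every case and control only the part predicted by the four covariates, compute the AUC, and bootstrap the interval with the model refitted each time.
3. If almost all screening women are dense (define this in advance), do not report the density-adjusted AUC. Report the AUC in dense women only and state that density cannot be separated from recruitment group.
4. Reconcile Sections 2 and 5 on which women the cutoffs come from.

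**Cost.** Two recorded items, one regression per primary parameter and some wording; recruitment and scheduling are unchanged. In simulation at a true AUC of 0.74, the standard error is 0.047-0.049 unadjusted and 0.050, 0.051 and 0.052 adjusted when 60%, 80% and 90% of screening women are dense. Those adjusted values are for a model without the benign indicator; expect similar or slightly larger values with it. The dense-only AUC has a standard error of 0.066-0.070. The 74% detectable-AUC statement applies to the unadjusted AUC only, and the plan should say so.
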